### 3.1 Primary Objectives

The primary objective of this study is to determine if there are clinically meaningful interactions between oral SXC-2023 treatment concurrent with 20 and 40 mg i.v. cocaine infusions by measuring adverse events (AEs) and cardiovascular responses including heart rate (HR), blood pressure (BP), and electrocardiogram (ECG) (including corrected QT interval [QTc]).

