## **7. STATISTICAL ANALYSES**

Descriptive statistics will be used to present study data. For continuous data, mean, standard deviation, median, 25th and 75th percentiles, minimum, and maximum will be presented. Categorical variables will be presented as counts and percentages. All data will be presented separately by treatment group. All data will be presented in listings, except for the assessments done to determine eligibility.

All the analyses of safety data for this study will be performed using SAS® statistical software package, version 9.4 or later. Additional software, such as R (version 4.5.1, The R foundation for Statistical Computing), may also be used for input data and TLFs generation if necessary.

Missing data will not be imputed for any analysis, except for partial dates for determining treatment emergent AEs and prior and concomitant medication (see [Section 7.1](#)). The numbers of data points reflected in summary statistics will be indicated by presenting the number of observations.

The pharmacokinetics data will be analyzed using Phoenix WinNonlin (Version 8.6 or later, Certara). Additional software such as R (version 4.3.3 or later, The R foundation for Computing) may also be used for input data and Tables, Listings, and Figures (TLFs) generation if necessary.

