#### 7.4.2 Cardiovascular Responses

Summary statistics (n, mean, standard deviation, median, minimum and maximum) of HR and BP by treatment, cocaine dose, infusion session, and timepoint will be presented. Maximum, maximum change and time to maximum from pre-infusion during the first hour after each infusion will be summarized by treatment, cocaine dose, and infusion session.

The maximum value and maximum change from pre-infusion values will be analyzed using an analysis of covariance (ANCOVA) model to compare the treatment groups (SXC-2023 versus placebo). The ANCOVA model will include the baseline (i.e., prior to SXC-2023/placebo treatment) maximum value or the baseline maximum change from pre-infusion as a covariate. The analyses for the 20mg and 40mg cocaine infusions will be performed separately. Effects will be considered statistically significant at a two-sided  $p < 0.05$ .

The distribution of the maximum value and maximum change for HR and BP will be explored. If not deemed normal or if right skewed, an ANCOVA analysis will be performed on the log-transformed HR and BP maximum value and maximum change. If the log-transformed data distribution is not normal then a Wilcoxon rank sum test will be used to compare treatment groups.

Time to maximum value will be analyzed using a Kaplan-Meier estimator. A log-rank test will be used to compare the time to maximum value by treatment groups (SXC-2023 vs Placebo). The analyses for the 20mg and 40mg cocaine infusions will be performed separately. Effects will be considered statistically significant at a two-sided  $p < 0.05$ .

ECG parameters extracted from Holter and their changes from pre-infusion (mean of the 3 pre-infusion ECGs) will be presented with summary statistics by visit and timepoint. Changes in ECG intervals during saline infusion as compared to those taken during cocaine infusions will be also reported as summary statistics. A listing of clinically significant ECG changes will be presented.

Pulse will be summarized by infusion session, timepoint, and treatment group.

Clinically significant ECG values will be presented in listings.

A listing of repeated assessments will be presented.

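### The HR/BP analysis can move to a log of maximum change that has no value at zero or below, and then to a Wilcoxon test without the baseline-session covariate

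*SAP*

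**What the plan says.** SAP 7.4.2 (Cardiovascular Responses) analyses the maximum HR and BP and the maximum change from pre-infusion, separately for 20 mg and 40 mg cocaine. The summaries cover the maximum, the maximum change and "time to maximum from pre-infusion during the first hour after each infusion". The group comparison is an ANCOVA that takes the baseline "maximum value or the baseline maximum change from pre-infusion as a covariate", where baseline means before SXC-2023 or placebo.

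The distribution of the outcome is then explored. "If not deemed normal or if right skewed", the plan changes: "an ANCOVA analysis will be performed on the log-transformed HR and BP maximum value and maximum change". A second change follows: "If the log-transformed data distribution is not normal then a Wilcoxon rank sum test will be used to compare treatment groups".

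Three things are not stated:

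- a test, threshold or decision-maker for either switch;
- an offset or rule for a change of zero or below;
- a baseline term in the Wilcoxon step.

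SAP section 7 adds "Missing data will not be imputed for any analysis", with an exception only for partial dates.

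**The concern.** **The log step.** The maximum change is a difference and can be zero or negative. Its log then does not exist. With no offset and no imputation, the participant would in practice leave that model. The loss is not random, because only those with no rise at all can be lost. If the covariate is logged too, which the SAP does not say, a non-positive change in the baseline session has the same effect.

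**The trigger.** Normality is judged on the outcome distribution, whereas the ANCOVA assumption concerns the residuals. The method is chosen after the outcome has been looked at, from about 16 to 20 values and with no written criterion.

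**The last step.** SAP 4.7.2.1 describes Sessions 2 and 3 as supplying each participant's cardiovascular response to cocaine without SXC-2023. The ANCOVA uses that information; the rank sum test does not. If baseline and treatment responses are well correlated, a primary safety comparison loses power just when the data are awkward.

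The SAP is firmer elsewhere. For PK (7.5.2.6) it fixes baseline-adjusted models in advance, says normality will not be checked, and reports a 95% CI.

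**Working it through.** **Inputs from the documents.** Twenty randomised, 10 per group, with 8 completers per group required (SAP 4.2). Each infusion has eight HR/BP readings in the following hour (SAP Table 4-5: 5, 10, 15, 20, 25, 30, 45 and 55 minutes after the first; 5 to 45 and 60 minutes after the second). The documents give no mean, SD, baseline correlation, effect size or power for HR or BP, so there is no planned figure to reproduce. Every value below is an assumption.

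**Step 1: who is exposed.** Maximum HR and BP are positive, so their logs always exist. A maximum change is at or below zero only if all eight readings fail to exceed the pre-infusion value.

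**Step 2: frequency on a normal distribution.** With mean rise m and SD s, p = Φ(−m/s). The chance of at least one such value among 16 is 1 − (1 − p)^16.

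| m / s | p | at least one of 16 |
|---|---|---|
| 25 / 10 | Φ(−2.50) = 0.6% | 10% |
| 10 / 6 | Φ(−1.67) = 4.8% | 54% |
| 8 / 6 | Φ(−1.33) = 9.1% | 78% |
| 10 / 8 | Φ(−1.25) = 10.6% | 83% |
| 8 / 8 | Φ(−1.00) = 15.9% | 94% |

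**Step 3: frequency under right skew.** The log branch can fire because of right skew, which thins the lower tail. Take a shifted gamma with skewness g: shape 4/g², scale s·g/2, location m − 2s/g.

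- m = 10, s = 6, g = 1: location −2, shape 4, scale 3, so p = 0.5% and the chance of any among 16 is 7.5%. At g = 1.5 the location is 10 − 8 = 2, so p = 0.
- m = 10, s = 8: the chance of any among 16 is 66% at g = 1 and 17% at g = 1.5.
- m = 8, s = 8, g = 1.5: location −2.67, shape 1.78, scale 6, so p is still about 11%.

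Clear skew therefore removes most of the problem when the mean rise is well above the SD, but not when the two are about equal.

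**Step 4: cost of the Wilcoxon step.** Simulated power at 8 per arm, two-sided 5%, shift 1.25 SD. Rank-ANCOVA regresses the ranked outcome on the ranked baseline plus treatment.

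| Baseline correlation | Normal: Wilcoxon vs rank-ANCOVA | Lognormal: Wilcoxon vs rank-ANCOVA |
|---|---|---|
| 0.3 | 63% vs 63% | 81% vs 82% |
| 0.5 | 62% vs 70% | 82% vs 86% |
| 0.7 | 61% vs 82% | 81% vs 92% |

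Simulated type I error stayed near 5% for each test taken singly.

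**The case against.** The strongest reply is that these are conditional branches behind a good default. Protocol 12.4.2 names the Wilcoxon rank sum test for HR and BP, so the last step returns to the protocol's method and the ANCOVA above it is already an improvement. Protocol 2.2.2.2 also cites dose-dependent rises in pulse and arterial pressure after comparable i.v. doses, which makes eight readings without a rise uncommon. Both arguments stand, and they limit the size of the point. They do not supply the missing rule for non-positive changes or justify dropping a covariate that the SAP chose to use.

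A reader might infer more than the documents support:

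- **That low responders will be removed.** Small positive changes stay in. Only values at or below zero are affected, and the exclusion itself is inferred from an undefined log plus no imputation.
- **That a loss is more likely than not.** The 54% to 94% entries in Step 2 are normal-tail results for assumed inputs. The same method gives 10% after a strong rise, and skew can bring it to zero.
- **That the arm difference shrinks by a known number of mmHg.** The log model estimates a ratio, so a truncated difference in raw means does not measure its bias.
- **That the baseline sessions are discarded.** They leave the between-group Wilcoxon test, but summaries by session and timepoint remain, and the maximum change still uses the same-day pre-infusion reading.
- **That type I error is inflated.** The simulations show no inflation for either test; the error of the whole switching procedure was not computed.

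Whether p < 0.05 answers an objective to "determine if there are clinically meaningful interactions between oral SXC-2023 treatment" is a separate matter, which follows from the sample size rather than from this sequence.

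**Conclusion.** The point holds as a defect in a stated rule of moderate consequence. As written, SAP 7.4.2 takes the log of a quantity that need not be positive, judges normality on the outcome rather than on residuals and without a threshold, and ends in a test that omits the baseline session.

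The frequency of undefined logs cannot be pinned down. It runs from near 0% to about 10-16% of maximum-change values, depending on the assumed ratio of mean rise to SD and on skew. The cost of the Wilcoxon step depends on the correlation between baseline and treatment sessions: nothing material at 0.3, about 8 percentage points of power at 0.5 and about 21 at 0.7 on normal data. On lognormal data rank-ANCOVA is also at least as good. None of these inputs is in the documents. The case for change rests on the missing rule and on the avoidable loss of the covariate, not on any one of these figures.

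**What to change.** Replace the fallback paragraph of SAP 7.4.2 with a fixed sequence:

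1. The primary analysis is ANCOVA on the untransformed maximum and maximum change, with the matching baseline-session value as covariate. Report the adjusted difference with its 95% CI.
2. Base any check of fit on the model residuals, with the criterion written down before unblinding.
3. Do not log-transform the maximum change.
4. If the check fails, use one named baseline-adjusted rank method, for example ranked outcome on ranked baseline plus treatment, in place of the unadjusted rank sum test. Another baseline-adjusted choice, such as a permutation test of the ANCOVA statistic, would also serve, provided that it is named in advance.

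The cost is a few sentences, with no new data, visits or participants. There are two small downsides. The rank test gives no estimate in mmHg or bpm, so the untransformed difference and CI should be shown alongside it. On skewed data the untransformed ANCOVA can have less power than the rank version, and where the baseline correlation is weak it may gain nothing over Wilcoxon; the rank fallback is there for that case.

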## 10.5 Cardiovascular Assessments During Infusion Sessions

Before and after each i.v. infusion, the participant's physiologic responses will be closely monitored using repeated HR, BP, and ECG readings, assessed in semi-supine position.

During the Screening Infusion Session 1, BP and HR will be recorded at the following nominal time points relative to the first infusion of the day: -30, -15, 5, 10, 15, 20, 25, 30, 45, 55, 65, 70, 75, 80, 85, 90, 105, 115, 125, 130, 135, 140, 145, 150, 165, 180, 210, 240, 270, 300, 330 and 360 minutes. Out of range BP and HR collected during the first 180 minutes post-dose will be repeated if deemed necessary by an investigator. Continuous cardiac monitoring with telemetry beginning approximately 60 minutes before the first infusion until 4 hours after the last cocaine infusion. Twelve-lead ECG measurements will be recorded at -30 minutes and at 5, 10, 15, 30, 45, 65, 70, 75, 90, 105, 125, 130, 135, 150, 165, 180, and 360 minutes after the first infusion. Study personnel and staff will monitor participants for at least 1 hour after each infusion. Times for collection of ECG and vital signs are nominal times  $\pm 3$  minutes for the first 30 minutes after the infusion and  $\pm 5$  minutes at all other time points. ECG then vital signs will be collected first when multiple assessments are scheduled at the same nominal time.

During the baseline and treatment infusions (Sessions 2 to 5), BP and HR will be recorded at the following time points relative to the first infusion of the day: -30, -15, 5, 10, 15, 20, 25, 30, 45, 55, 65, 70, 75, 80, 85, 90, 105, 120, 150, 180, 210, 240, 270, and 300 minutes. Out of range BP and HR collected during the first 180 minutes post-dose will be repeated if deemed necessary by an investigator. Continuous cardiac monitoring with telemetry beginning approximately 60 minutes before the first infusion until 4 hours after the second infusion. Twelve-lead ECG measurements will be recorded at -30 minutes and at nominal 5, 10, 15, 30, 45, 65, 70, 75, 90, 120, 150, 180 and 300 minutes after the first infusion. Times for collection of ECG and vital signs are nominal times  $\pm 3$  minutes for the first 30 minutes after the infusion and  $\pm 5$  minutes at all other time points. ECG then vital signs will be collected first when multiple assessments are scheduled at the same nominal time.

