## 4.4 Stopping Criteria

### 4.4.1 Study

The study will be halted from further enrollment if any of the following criteria are met at any point during the study:

- Four participants experience a severe AE, such as significant neurological or psychiatric events (e.g., psychosis) or behavioral manifestations of cocaine toxicity
- Two severe AEs related to cocaine toxicity
- Two participants experience a similar SAE that is not clearly unrelated to study drug or cocaine
- Two participants fulfill the following ECG criteria based on the mean of triplicate measures ( $\geq 1$  minute apart), that will be completed once the first ECG demonstrates a prolonged interval: QTcF  $\geq 500$  msec or uncorrected QT interval of  $> 600$  msec.

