## **5. STUDY ENDPOINTS**

### **5.1 Primary Endpoints**

The primary endpoints are adverse events (AEs) and cardiovascular responses including HR, BP, and ECG (including QTcF).

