#### **5.1.2 Cardiovascular and Blood Pressure Assessments**

Before and after each i.v. infusion, the participant's physiologic responses will be closely monitored using repeated HR, BP, and ECG readings assessed in semi supine position.

During the Screening Infusion Session 1, BP and HR will be recorded at the following nominal time points relative to the first infusion of the day: -30, -15, 5, 10, 15, 20, 25, 30, 45, 55, 65, 70, 75, 80, 85, 90, 105, 115, 125, 130, 135, 140, 145, 150, 165, 180, 210, 240, 270, 300, 330 and 360 minutes. Out of range BP and HR collected during the first 180 minutes post-dose will be repeated if deemed necessary by an investigator. Continuous cardiac monitoring with telemetry will begin approximately 60 minutes before the first infusion and will end 4 hours after the last cocaine infusion. Twelve-lead ECG measurements will be recorded at -30 minutes and at 5, 10, 15, 30, 45, 65, 70, 75, 90, 105, 125, 130, 135, 150, 165, 180, and 360 minutes after the first infusion. Study personnel and staff will monitor participants for at least 1 hour after each infusion. Times for collection of ECG and vital signs are nominal times  $\pm$  3 minutes for the first 30 minutes after the infusion and  $\pm$  5 minutes at all other time points. ECG, then vital signs will be collected first when multiple assessments are scheduled at the same nominal time.

During the baseline and treatment infusions (Sessions 2 to 5), BP and HR will be recorded at the following time points relative to the first infusion of the day: -30, -15, 5, 10, 15, 20, 25, 30, 45, 55, 65, 70, 75, 80, 85, 90, 105, 120, 150, 180, 210, 240, 270, and 300 minutes. Out of range BP

and HR collected during the first 180 minutes post-dose will be repeated if deemed necessary by an investigator. Continuous cardiac monitoring with telemetry beginning approximately 60 minutes before the first infusion until 4 hours after the second infusion. Twelve-lead ECG measurements will be recorded at -30 minutes and at nominal 5, 10, 15, 30, 45, 65, 70, 75, 90, 120, 150, 180 and 300 minutes after the first infusion. Times for collection of ECG and vital signs are nominal times  $\pm 3$  minutes for the first 30 minutes after the infusion and  $\pm 5$  minutes at all other time points. ECG, then vital signs will be collected first when multiple assessments are scheduled at the same nominal time.

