ECG measurements to be recorded on a CRF include HR, RR, PR, QRS, and QT interval. For data analysis the QT interval will be corrected using the method of Fridericia (1920) (QTcF).

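### The SAP measures ECG/QTcF change from a mean of three pre-infusion Holter ECGs that neither schedule provides, and QTcF, part of the primary endpoint, has no formal between-arm estimate

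*SAP*

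**What the plan says.** SAP 5.1 sets the primary endpoint: "The primary endpoints are adverse events (AEs) and cardiovascular responses including HR, BP, and ECG (including QTcF"). Protocol 12.1.1 agrees.

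For ECG collection in Sessions 2 to 5, Protocol 10.5 states: "Twelve-lead ECG measurements will be recorded at -30 minutes and at nominal 5, 10, 15, 30, 45", continuing at 65, 70, 75, 90, 120, 150, 180 and 300 min. SAP 5.1.2, Protocol Table 4 and SAP Table 4-5 give the same times. SAP 5.1.2 adds "Continuous cardiac monitoring with telemetry beginning approximately 60 minutes before the first infusion until 4 hours after the second infusion", and says that "ECG measurements to be recorded on a CRF include HR, RR, PR, QRS, and QT interval", with QTcF derived from that QT.

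For ECG analysis, SAP 7.4.2 says: "ECG parameters extracted from Holter and their changes from pre-infusion (mean of the 3 pre-infusion ECGs) will be presented". It then plans summaries by visit and timepoint, a descriptive contrast of saline with cocaine, and listings. In the same section, the maximum and maximum change that are defined for HR and BP are "analyzed using an analysis of covariance (ANCOVA) model to compare the treatment groups (SXC-2023 versus placebo"), with the pre-treatment value as covariate.

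Triplicate ECGs appear in one other place, the study stopping rule (SAP 4.4.1, Protocol 9.12), as a repeat "that will be completed once the first ECG demonstrates a prolonged interval".

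**The concern.** The analysis sentence describes data that the schedules do not generate. It names a source (Holter) found nowhere else in either document and a baseline (three ECGs averaged) that no session contains. Whoever programs the analysis must choose another baseline, and the choice changes every QTcF change value.

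The second issue is the comparison. The primary objective asks whether SXC-2023 interacts with cocaine on cardiovascular responses, QTcF included. For HR and BP the SAP answers with a baseline-adjusted arm difference. For QTcF it offers tables to compare by eye. The contrast between saline and cocaine infusions describes what cocaine does, not whether SXC-2023 changes it. With 8 to 10 participants per arm, two similar-looking columns could be taken as showing no interaction when nothing states how large a difference remains compatible with the data.

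**Working it through.** **Can three pre-infusion ECGs be found?** Scheduled ECG times for Sessions 2 to 5, in minutes from the first infusion: -30, 5, 10, 15, 30, 45, 65, 70, 75, 90, 120, 150, 180, 300. The second infusion is at 60.

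- Before the first infusion: one (-30).
- Before the second infusion: six (-30, 5, 10, 15, 30, 45), of which five follow the first infusion.
- In the half-hour before the second infusion: two (30 and 45).

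No within-session count gives the SAP's figure of three. Across days, three can be assembled from the -30 min ECGs of Days -2, 1 and 2, or from screening, intake and Day -2. The SAP states neither reading, and both use 12-lead ECGs, not Holter.

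**Which baseline serves both infusion orders?** In cocaine-first participants the 30 and 45 min ECGs follow cocaine, so using them as the pre-saline reference would contaminate it. Only the -30 min ECG precedes both infusions in either order. In saline-first participants it lies 60 - (-30) = 90 min before cocaine.

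**Which post-cocaine times are comparable?** Cocaine first: 5, 10, 15, 30, 45 min after infusion. Cocaine second (65, 70, 75, 90, 120 min less 60): 5, 10, 15, 30, 60 min. The common set is 5, 10, 15 and 30 min.

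**What does a single-ECG baseline cost?** Let s be the within-subject SD of one QTcF reading, with independent errors of equal variance. The SD of a change at one timepoint is s√(1 + 1/k) for a baseline averaged over k ECGs. The documents give no s; 5 to 10 ms is assumed.

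| s (ms) | k = 1 | k = 3 |
|---|---|---|
| 5 | 7.1 | 5.8 |
| 8 | 11.3 | 9.2 |
| 10 | 14.1 | 11.5 |

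The ratio is √2 / √(4/3) = √1.5 = 1.22 for any s.

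**How precise would an arm difference be?** The 95% half-width is t(0.975, 2n - 2) × SD × √(2/n), before covariate adjustment. The SD of change across participants is assumed to be 8 to 15 ms, since the documents give none.

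- n = 8 per arm: 2.145 × 8 × 0.5 = 8.6 ms, to 2.145 × 15 × 0.5 = 16.1 ms.
- n = 10 per arm: 2.101 × 8 × 0.447 = 7.5 ms, to 2.101 × 15 × 0.447 = 14.1 ms.

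For an illustrative 10 ms difference (two-sided 0.05, normal approximation), power falls from 0.71 to 0.27 at 8 per arm, and from 0.80 to 0.32 at 10 per arm, over that SD range.

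**Formal between-arm QTcF analyses specified in the SAP:** none. The ANCOVA paragraph follows the HR and BP summaries, and its distribution check names only HR and BP.

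**The case against.** The best defence is that descriptive ECG output was always the plan. Protocol 12.4.2 tests HR and BP and gives ECG intervals summary statistics only. Adverse events, also primary, are descriptive too. Nothing in the documents ties primary status to a formal test, and with 8 to 10 per arm and no power basis a test would decide little. This stands in part. The SAP did not drop a planned between-arm ECG test, and the gap is against the stated objective. It is a reason to report an interval rather than a p-value.

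Three stronger readings are tempting, and the documents do not support them.

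- That QTcF will not be compared between arms at all. SAP 7 presents all data by treatment group, so summaries will appear by arm. What is missing is an estimate with its uncertainty.
- That the QTcF result cannot be computed. Absolute QTcF at each scheduled time can be. Only change from the stated baseline cannot. Telemetry does run before the infusion, and the Manual of Procedures and the separate table list are not available here, so an unlisted recording is possible. But no available text describes extracting ECGs from telemetry.
- That the baseline will be picked after the data are seen. Nothing says so; the SAP simply leaves the choice open.

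It can also be said that the protocol already requires an ECG in the half-hour before any cocaine infusion. It does, as a check before dosing, but that does not supply three readings or define an analysis baseline. Finally, the 22% assumes independent errors. Closely spaced triplicates may be correlated, which would shrink the advantage of averaging.

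**Conclusion.** The SAP sentence is wrong as it stands: for a variable in the primary endpoint, it defines change from a baseline that the scheduled data do not contain. This follows from counting ECG times and needs no assumption. Separately, QTcF lacks a between-arm estimate or confidence interval, so the interaction question is left to visual comparison. There is also a smaller departure from the protocol: Protocol 12.4.2 promises counts and percentages of clinically significant ECG changes, and SAP 7.4.2 provides listings only.

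The figures in milliseconds rest on assumed SDs. The 22% is exact under independent, equal-variance errors and applies to change at a single timepoint, not to a maximum over several. It is a cost of the available baseline, not a gain from the correction.

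**What to change.** Before unblinding, replace the ECG sentence in SAP 7.4.2 as follows.

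- **Source and baseline:** the scheduled 12-lead ECGs, with the session's -30 min ECG as baseline for both infusions. If Holter or triplicate ECGs are in fact collected, add them and their extraction times to the protocol and SAP schedules instead.
- **Between-arm estimate:** for each cocaine dose, the SXC-2023 minus placebo difference in maximum QTcF change after cocaine, over 5, 10, 15 and 30 min, from the HR/BP ANCOVA already written. The covariate is the matching Day 1 (20 mg) or Day 2 (40 mg) value. Report the 95% CI and label the result as an estimate, not a decisive test.
- **Categories:** by arm, counts of QTcF above 450 ms (the protocol's exclusion limit) and at or above 500 ms (its stopping limit), used here only as reporting thresholds. Restore the protocol's counts and percentages of clinically significant ECG changes.

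The cost is SAP wording and added table output, with no new procedures under the 12-lead option. The drawbacks should be stated in the SAP: a noisier baseline than the one now claimed, a 90-minute gap before cocaine in saline-first participants, the exclusion of the 45 and 60 min readings from the maximum, and an imprecise arm difference. The -30 min baseline also does not remove residual cocaine from the saline window of cocaine-first participants, so the saline contrast needs that caveat.
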